6. SUB-STUDY PROCEDURES

Subjects from the long term extension study who elect to participate in the sub-study should complete a combined A3921092 Sub-study Switch/Baseline visit on the same day of the scheduled A3921092 study visit at or after Month 24.

The study investigator or a sub-investigator will discuss with each subject the nature of the study, its requirements, and its restrictions. Written informed consent must be obtained prior to performance of any protocol-specific procedures.

Subjects who are on prohibited medications, and are deriving a beneficial response from them, should not be entered into this sub-study. Subjects may be discontinued from the sub-study at any time during the sub-study in the event of deterioration of response as determined by the investigator.

6.1. Combined A3921092 & Sub-Study Switch/Baseline Visit

The Combined A3921092 Sub-study Switch/Baseline visit occurs at Month 24, Month 27, Month 30, Month 33, or Month 36 of A3921092. Since not all of the study procedures and assessments needed for the Baseline of the sub-study are collected at these visits of A3921092, any assessment or activity that was not completed as part of the A3921092 visit needs to be completed at this combined visit. At the Switch/Baseline visit of the sub-study, all investigational product from the main A3921092 LTE study will be collected for accountability under the main protocol. New tofacitinib supplies will be dispensed under the sub-study. Details of the required activities are listed below.

Subjects are required to fast for at least 9 hours prior to the visit. Blood collection may be taken up to 48 hours prior to or following this visit as necessary to ensure samples are collected in a fasted state.

All Patient Reported Outcomes should be completed prior to any other study procedures.

6.1.1. Combined A3921092 & Sub-Study Switch/Baseline Visit at Month 24 or Month 36

For subjects with the Combined A3921092 Sub-study Switch/Baseline visit conducted at the scheduled A3921092 study visit of Month 24 (M24) or Month 36 (M36), subjects must complete activities as indicated from M24 or M36 visit of A3921092 in addition to the following procedures:

- Informed consent obtained.
- Collect tofacitinib LTE investigational product supplies and complete accountability for the last visit of the main LTE study.
- Register for subject identification number.
- Randomization completed.
- Dispense study medication/schedule next visit.
- Observe subject taking the study drugs (tofacitinib and MTX or placebo) and record the dosing in the dosing log CRF.

6.1.2. Combined A3921092 & Sub-Study Switch/Baseline Visit at Month 27 or Month 33

For subjects with the Combined A3921092 Sub-study Switch/Baseline visit conducted at the scheduled A3921092 study visit of Month 27 or Month 33, the subjects must complete activities as indicated from M27 or M33 visit of A3921092 in addition to the following procedures.

- Informed consent obtained.
- Collect tofacitinib LTE investigational product supplies and complete accountability for the last visit of the main LTE study.
- Register for subject identification number.
- Randomization completed.
- SF-36 Version 2 (Acute).
- FACIT-F.
- EQ-5D.

The following additional procedures will also be performed:

- Cardiovascular Risk Assessment: smoking status, average weekly alcohol consumption and family history of premature coronary heart disease (see [Section 7.4](#) of LTE study).
- Physical Examination: Complete physical examination (height, weight, general appearance) skin (presence of rash), HEENT (head, eyes, ears, nose and throat), lungs (auscultation), heart (auscultation for presence of murmurs, gallops, rubs), extremity exam (presence of peripheral edema), abdomen (palpation and auscultation), neurologic (mental status, station, gait, reflexes, motor and sensory function, coordination) and lymph nodes.
- Waist and hips circumference.
- Blood testing: Central laboratory testing of Lipid Profile (fasting).
- Yearly TB testing if applicable.
- 12-lead electrocardiogram.
- Monitoring of adverse events and concomitant treatments. Record any modifications, deletions or additions.

- Drug dispensing.
- Observe subject taking the study drugs (tofacitinib and MTX or placebo) and record the dosing in the dosing log CRF.

6.1.3. Combined A3921092 & Sub-Study Switch/Baseline Visit at Month 30

For subjects with the Combined A3921092 Sub-study Switch/Baseline visit conducted at the scheduled A3921092 study visit of Month 30, the subjects must complete activities as indicated from M30 visit of A3921092 in addition to the following procedures at the combined screening/baseline visit.

- Informed consent obtained;
- Collect tofacitinib LTE investigational product supplies and complete accountability for the last visit of the main LTE study.
- Register for subject identification number.
- Randomization completed.

The following additional procedures will also be performed:

- Physical Examination: Complete physical examination (height, weight, general appearance) skin (presence of rash), HEENT (head, eyes, ears, nose and throat), lungs (auscultation), heart (auscultation for presence of murmurs, gallops, rubs), extremity exam (presence of peripheral edema), abdomen (palpation and auscultation), neurologic (mental status, station, gait, reflexes, motor and sensory function, coordination) and lymph nodes.
- 12-lead electrocardiogram.
- Yearly TB testing if applicable.
- Monitoring of adverse events and concomitant treatments. Record any modifications, deletions or additions.
- Drug dispensing.
- Observe subject taking the study drugs (tofacitinib and MTX or placebo) and record the dosing in the dosing log CRF.

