6.1.1.2. Baseline Visit

This visit must occur 2-28 days after screening visit.

Subjects are required to fast for at least 9 hours prior to the visit, however, blood collection for laboratory testing may be taken up to 48 hour prior to the Baseline/Day 0 visit as necessary to ensure the samples are collected in a fasting state.

All Patient Reported Outcomes should be performed before any other study procedures. These include the following:

- Patient's Assessment of Arthritis Pain (VAS).
- Patient's Global Assessment of Arthritis (VAS).
- Health Assessment Questionnaire – Disability Index (HAQ-DI).
- BASDAI.
- ASQOL.
- Patient's Global Joint and Skin Assessment (PGJS-VAS).
- SF-36 Version 2 (Acute).
- DLQI.
- FACIT Fatigue Scale.
- EuroQol 5 Dimensions (EQ-5D).
- ISI.
- WLQ.
- PsA-HCRU.

Procedures that will be performed prior to enrollment and the first dose of study drug on Visit 1, Day 1 for baseline include:

- Targeted Physical Examination: (weight, examination of hearts, lungs, abdomen, lower extremities and lymph nodes).
- Vital signs: blood pressure, pulse rate and temperature (tympanic, oral or temporal preferred).

- Waist and hips circumference.
- Blood and urine specimen testing: Central laboratory tests include: Hematology, Chemistry Panel, Lymphocyte subset analysis (FACS), Hemoglobin A1c (HbA1c), C-Reactive Protein (CRP), Lipid Profile (fasting), Urinalysis.
- Urine Pregnancy Test (for women of childbearing potential only).
- Clinical Evaluation of Rheumatology Endpoints:
 - Tender/painful joint counts (68);
 - Swollen joint counts (66);
 - Physician's Global Assessment of Arthritis (VAS);
 - Assessment of presence and severity of dactylitis;
 - Assessment of enthesitis using the Spondyloarthritis Research Consortium of Canada (SPARCC) Enthesitis Index and Leeds Enthesitis Index.
- Clinical Evaluation of Dermatology Endpoints:
 - Physician's Global Assessment of Psoriasis (PGA-PsO);
 - Psoriasis Area and Severity Index (PASI);
 - Body Surface Area (BSA);
 - Nail Psoriasis Severity Index (NAPSI).
- Clinical Evaluation of Rheumatology and Dermatology Endpoint: Physician's Global Assessment of Psoriatic Arthritis (VAS).
- Drug dispensing.
- Monitoring of adverse events and concomitant treatment.

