9.3. Efficacy Analysis

The Full Analysis Set (FAS) will include all subjects who were randomized to the sub-study and received at least one dose of the sub-study drug (tofacitinib, MTX or placebo). The primary efficacy population for this study is defined by the FAS.

Continuous endpoints for which change or percent change from baseline is the measure to be analyzed, would require that a subject have a baseline value and at least one post-baseline value to be included in the FAS for that endpoint.

For all the efficacy and PRO endpoint analyses, the baseline will be the latest value obtained prior to the first dose of the sub-study.

Continuous endpoints collected over multiple visits (eg, Δ HAQ-DI or Δ PASDAS) will be analyzed using a Mixed Model for Repeated Measures (MMRM) without imputation for missing values on the FAS. Treatment comparison between the 2 groups at each post-baseline time point will be generated from this model providing both 2-sided p-value and 95% CI.

Binary endpoints (eg, MDA response) will be analyzed using the normal approximation for the difference in binomial proportions with missing response as non-response (MR=NR) on the FAS. Treatment comparison between the 2 groups at each post-baseline time point will be generated providing both 2-sided p-value and 95% CI.

Efficacy will also be assessed for a subset of the subjects who had more severe PsA as defined by ≥ 5 swollen or tender joints at the baseline of the sub-study, if sample size permits.

Complete details will be specified in the SAP.

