Appendix 2.9. Psoriatic Arthritis Disease Activity Score (PASDAS)

PASDAS (Helliwell et al 2013)⁶ is a composite PsA disease activity score that includes the following components: patient global joint and skin assessment (VAS in mm), physician global psoriatic arthritis assessment (VAS in mm), swollen (66 joints) and tender joint counts (68 joints), Leeds Enthesitis Index score, tender dactylitic digit score, physical component summary score (PCS) of SF-36v2 and CRP (mg/L).

$$\begin{aligned} \text{PASDAS} = & (((0.18 \times \sqrt{\text{Physician global VAS}}) + (0.159 \times \sqrt{\text{Patient global VAS}}) \\ & - (0.253 \times \sqrt{\text{SF36-PCS}}) + (0.101 \times \text{LN}(\text{Swollen joint count} + 1)) \\ & + (0.048 \times \text{LN}(\text{Tender joint count} + 1)) \\ & + (0.23 \times \text{LN}(\text{Leeds enthesitis index score} + 1)) \\ & + (0.37 \times \text{LN}(\text{Tender dactylitis count} + 1)) \\ & + (0.102 \times \text{LN}(\text{CRP} + 1)) + 2) \times 1.5 \end{aligned}$$

where LN() is the natural logarithm. For patient’s global joint and skin assessment (VAS), it is obtained only from the first question in the CRF for assessing subject’s global joint and skin, “In all the ways in which your PSORIASIS and ARTHRITIS, as a whole, affects you, how would you rate the way you felt over the past week?” The physician’s global psoriatic arthritis assessment (VAS) is obtained from the CRF at the prompt: “THE SUBJECT’S OVERALL PSORIATIC ARTHRITIS AT THIS TIME IS...”. The tender dactylitis digit score is the number of digits out of 20 (fingers and toes) where rating of either 2 (digit is tender and swollen (active)) or 3 (digit is very swollen and tender or very tender and swollen (highly active)) is registered. Any missing component will result in PASDAS as missing. The VAS data will need to be rescaled prior to any calculation (Section 6). A higher PASDAS score indicates a higher disease activity.

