5. ENDPOINTS AND COVARIATES

Visual analog scale (VAS) data will be similarly rescaled prior to any calculation and analysis as in the main LTE study. Refer to main LTE study [Section 6](#) for the details. *The baseline will be the latest value obtained prior to the first dose of the sub-study.*

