7.4. Sub-study Definition and Use of Visit Windows in Reporting

The visit windows are similarly defined as for the main LTE study in below table. The study day will be calculated as: date of assessment/collection – date of the first dose in the sub-study + 1.

If two or more visits/observations fall into the same window, the visit/observation closest to the target day should be used in the analyses. If there is a tie, the later visit should be used. However, if two or more visits/observations fall in the same window, and the latest visit is the last visit of the study due to early termination, then this will be the visit used in the analysis for that visit window. Per the master visit schedule provided to the investigator sites, a month is defined as 4 weeks or 28 days.

Visit Label	Target Day	Definition [Day Window] – Lower	Definition [Day Window] - Upper
Switch/Baseline	1	Day 1 = date of first dose of study treatment taken of sub-study Prior to first dose of study treatment taken of sub-study	
Month 1	29	2	57
Month 3	85	58	127
Month 6	169	128	211
Month 9	253	212	295
Month 12	337	≥296	

The following categories will be used in the treatment exposure and duration of treatment summaries for tofacitinib. The duration of treatment will be calculated as: date of the last dose in the sub-study – date of the first dose in the sub-study + 1. Any missed doses/drug holidays will be ignored in the duration calculation. Treatment exposure will be defined as the number of days that subjects took the study drug (gaps not counted).

Category (days)
1
2-28 (1 month)
29-84 (1-3 months)
85-168 (3-6 months)
169-252 (6-9 months)
≥253 (9-12 months)

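### Sub-study baseline blood may be drawn up to 48 hours after the observed first dose, so CRP, and through it PASDAS (one of two primary endpoints), can lack a same-visit pre-dose baseline

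*Protocol*

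**What the plan says.** **Blood sampling and first dose.** Appendix 10 Section 6.1 covers the combined switch/baseline visit and says: "Blood collection may be taken up to 48 hours prior to or following this visit as necessary to ensure samples are collected in a fasted" [...]. The sentence refers to blood collection in general, not to lipids alone. For every entry month (24, 27, 30, 33 or 36), Sections 6.1.1 to 6.1.3 end with the same instruction: "Observe subject taking the study drugs (tofacitinib and MTX or placebo) and record the dosing in the dosing log CRF". Appendix 10 Section 3 adds that the sub-study has no baseline visit of its own.

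**Definition of baseline.** For efficacy, Appendix 10 Section 9.3 states that "the baseline will be the latest value obtained prior to the first dose of the sub-study". Section 9.4 applies the same rule to safety, and SAP Appendix 6 Section 5 repeats it. The baseline row of the visit-window table in SAP Appendix 6 Section 7.4 reads "Prior to first dose of study treatment taken of sub-study". It sets no lower day limit, and the Month 1 window opens on Day 2.

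**Consequence of a missing CRP.** CRP is a PASDAS component, and SAP Appendix 2.9 says "Any missing component will result in PASDAS as missing". Under SAP Appendix 6 Section 7.2, a change-from-baseline endpoint needs both a baseline and at least one later value for the subject to be in the FAS.

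**The main study's own separate baseline visit.** Protocol Section 6.1.1.2 allows earlier draws only: "blood collection for laboratory testing may be taken up to 48 hour prior to the Baseline/Day 0 visit".

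**The concern.** The switch visit is the only chance to obtain a sub-study baseline. The protocol permits a sequence (dose today, bleed tomorrow) in which the sample meant to serve as baseline cannot qualify under the protocol's own definition. A pre-dose sample that was never taken cannot be recovered.

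Change in PASDAS at Month 6 is the most important quantity at stake. Change in CRP and change in DAS28-3 (CRP) are exposed in the same way. So is laboratory safety follow-up. Appendix 10 Section 7.6.7 sets a new laboratory baseline at the switch visit, except for the Hy's law assays. Sections 7.6.9.1 and 7.6.9.2 then compare hemoglobin and creatinine with the sub-study baseline, described as its first day.

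**Working it through.** **1. Order of events for a subject bled after the visit**

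- Day 1: switch visit, randomization, observed first dose of tofacitinib and MTX/placebo.
- Up to 48 hours later (Day 3 at the latest): blood for CRP, hematology, chemistry and lipids.
- The sample follows the first dose, so it is not baseline. If taken on Day 2 or 3 it lies in the Month 1 window (Days 2 to 57), and would be used there only if no observation nearer Day 29 existed.

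**2. What baseline PASDAS then becomes**

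The documents leave three readings open:

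- *Missing.* CRP is absent at the switch visit, so PASDAS is missing and the subject leaves the FAS for it. SAP Appendix 6 Section 7 (sub-study data only) and Section 7.3.1 (baseline summaries from the combined visit) point this way.
- *CRP alone carried in.* Protocol Section 7.2.9 has CRP drawn at every visit, so the last earlier value is about 3 months old. The other components come from the switch visit.
- *Whole PASDAS carried in.* PASDAS needs the SF-36 physical component, and Type B visits (Protocol Section 6.2.2) do not collect SF-36. The last complete earlier score is therefore:

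| Entry month | Last earlier visit with SF-36 | Age |
|---|---|---|
| 24 | 18 | 6 months |
| 27 | 24 | 3 months |
| 30 | 24 | 6 months |
| 33 | 30 | 3 months |
| 36 | 30 | 6 months |

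Appendix 10 Section 4.1 requires a subject on 10 mg BID to reduce 3 months before randomization, and a subject on non-oral MTX to switch at least 12 weeks before entry. For some subjects an older score could therefore reflect different treatment.

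**3. Precision**

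Inputs from Appendix 10 Section 9.1: 90 per group, SD 1.6 for PASDAS and 0.6 for HAQ-DI, two-sided 95%.

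Half-width = 1.96 × SD × √(2/n).

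- PASDAS as planned: 1.96 × 1.6 × √(2/90) = 0.4675. Stated: 0.47, reproduced.
- HAQ-DI as planned: 1.96 × 0.6 × √(2/90) = 0.1753. Stated: 0.18, reproduced.

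If a share f of each arm loses its PASDAS baseline, n becomes 90(1 − f). The documents give no f, so the values below are assumptions.

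| f | Subjects lost of 180 | n per group | PASDAS half-width |
|---|---|---|---|
| 0 | 0 | 90 | 0.47 |
| 5% | 9 | 85.5 | 0.48 |
| 10% | 18 | 81 | 0.49 |
| 20% | 36 | 72 | 0.52 |

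HAQ-DI uses no blood sample, so its half-width does not change.

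**4. How much an older CRP could move PASDAS**

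SAP Appendix 2.9 gives the CRP term as 1.5 × 0.102 × ln(CRP + 1), with CRP in mg/L.

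- 10 instead of 2.87 (the upper limit of normal in SAP Appendix 2.1): 0.153 × [ln 11 − ln 3.87] = 0.16.
- 20 instead of 1: 0.153 × [ln 21 − ln 2] = 0.36.

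Both are small against the SD of 1.6. The damage comes mainly from the missing-component rule, not from the CRP value.

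**The case against.** Two other passages favor a pre-dose draw. The switch visit is also a scheduled extension visit, and Protocol Section 6.2 says a visit at which the subject has not fasted should be rescheduled within 48 hours. Appendix 10 Section 4.3 makes enrollment conditional on the switch-visit procedures having been done. Followed together, these would prevent the problem sequence. They reduce the risk without removing it. Section 6.2 grants the same after-visit allowance immediately before its rescheduling rule. The corresponding rule in Appendix 10 Section 6.2 names only Months 1, 3, 6, 9 and 12. Section 4.3 conflicts with Section 6.1 but does not override it.

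CRP itself needs no fasting. Fasting is tied to the lipid panel (Protocol Section 4.4.4 and Appendix 10 Section 4.4.4), and the allowance applies only where needed to obtain fasted samples. A site could draw CRP at the visit and defer lipids alone. This stands, and it is a good reason to expect few cases. But Section 6.1 does not split the draw, and nothing requires CRP before dosing.

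A reader might infer that affected subjects are necessarily excluded, or necessarily measured against a 3-to-6-month-old score under other treatment. The documents support neither as a certainty. Carrying in CRP alone is also possible and would change PASDAS little, and the treatment difference arises only in subjects who had recently reduced tofacitinib or changed MTX route.

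**Conclusion.** The gap is real and is written into the protocol: the sampling allowance at the switch visit contradicts the definition of baseline, and the SAP does not say what replaces a baseline sample taken too late. It touches one of the two primary endpoints, two further efficacy endpoints and the laboratory references for safety follow-up.

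The likely effect is modest. With an assumed 5% to 20% loss in both arms, the PASDAS half-width rises from 0.47 to between 0.48 and 0.52. The true share is unknown and probably near or below the lower end, because the allowance is conditional on fasting.

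A reader might go further and infer bias in the treatment comparison. The documents do not support that: MTX assignment is blinded and nothing links the timing of the draw to the arm. Nor is this a sub-study with co-primary hypotheses at risk. It is an estimation study with two primary endpoints and no formal tests of hypotheses, and HAQ-DI is untouched.

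**What to change.** In Appendix 10 Section 6.1, delete *or following* for the combined switch/baseline visit. State that CRP, hematology, chemistry and lipids must be drawn before the first sub-study dose, and may be drawn up to 48 hours before the visit, as Protocol Section 6.1.1.2 already allows for the main study's baseline.

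State also that, for sub-study entrants, this overrides the after-visit allowance in Protocol Sections 6.2, 6.2.3 and 6.2.4. Without that sentence the allowance returns, because switch-visit CRP and most of the safety blood come from the extension visit's own activities. Keep the allowance for post-baseline visits.

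As a backstop, one sentence in SAP Appendix 6 Section 5 should say whether an earlier extension-study value may serve as baseline, and if so whether by component or only as a complete score.

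The cost is a few sentences. In practice, an unfasted subject's switch visit moves by up to 2 days, which Protocol Section 6.2 already provides for.

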5.1. Sub-Study Allocation to Treatment

The following medication will be supplied by Pfizer Inc:

- Tofacitinib 5 mg tablets (open-label).
- Methotrexate 2.5 mg capsules.
- Placebo capsules that match Methotrexate capsules.

Both the open-label tofacitinib 5 mg and blinded MTX will be dispensed to subjects to self-administer after appropriate training and specific written instructions are provided. Tofacitinib will be taken orally 5 mg BID (approximately every 12 hours). Methotrexate or MTX placebo will be taken orally once a week. The dose of MTX must be the same oral dose as taken prior to sub-study entry; allowed doses of MTX entry may range from 7.5 mg to a maximum of 20 mg a week but must be stable 4 weeks prior to entering the sub-study, and must not be changed with the following exception. Reductions in the dose of MTX are permitted if there is evidence of toxicity. For subjects who are on a MTX dose higher than 7.5 mg per week, the MTX dose may be reduced to 7.5 mg per week on one occasion and with Sponsor's approval. Dose re-adjustments of MTX will be allowed with Sponsor's approval. Reductions of tofacitinib dose are not permitted. Temporary withdrawals of any of the sub-study drugs (tofacitinib and methotrexate/placebo) are only permitted if required

due to safety concerns. Study treatment will continue until the subject discontinues from the study or has received approximately 12 months of treatment.

Allocation of subjects to treatment will proceed through the use of an interactive response technology (IRT) system (interactive Web-based response (IWR)). During the sub-study Baseline visit, the site personnel (study coordinator or specified designee) will be required to enter or select information including but not limited to the user's identification (ID) and password, the protocol number, and the subject's number. The site personnel will then be provided with a randomization number and container number(s) when investigational product is being supplied via the IRT system. The confirmation report must be stored in the site's files.

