5.4. Sub-Study Administration

All investigational products will be self-administered by the subject as specified in the dosing card. Tofacitinib should be administered orally, twice daily, approximately 12 hours apart, once in the morning and once in the evening. During the sub-study all subjects will receive a dose of 5 mg BID taking 1 tablet in the morning and 1 tablet in the evening. If a tofacitinib dose is missed and the interval to the next scheduled dose is less than 6 hours, the missed dose of tofacitinib should not be administered.

At the time of enrollment (eg, the Combined A3921092 Sub-study Switch/Baseline visit), subjects must discontinue the use of their personal (commercial) supply of MTX. MTX or its matching placebo will be provided by the Sponsor and must be administered orally once a week (the same day of the week) in a predetermined dose that may range from 7.5 mg/week to 20 mg/week. Subjects will receive the corresponding number of MTX or matching placebo 2.5 mg capsules to complete their individual preselected dose of oral MTX (Sub-Study [Table 3](#)). Subjects should be instructed to document any missed doses.

Sub-Study Table 3

Assigned Dose of MTX	Corresponding number of MTX 2.5 mg capsules or matching placebo
7.5 mg/week	3 capsules
10 mg/week	4 capsules
12.5 mg/week	5 capsules
15 mg/week	6 capsules
17.5 mg/week	7 capsules
20 mg/week	8 capsules

Subjects who are randomized to tofacitinib 5 mg BID + MTX placebo will experience a full withdrawal of MTX (eg, no tapering) at the time of randomization.

Study medications may be administered with or without food, with exception of the day of the study visits that require fasting.

Medication errors may result in the sub-study from the administration or consumption of the wrong product, by the wrong subject, at the wrong time, or at the wrong dose. Such medication errors occurring to a study participant are to be captured on the adverse event page of the CRF and on the SAE form when appropriate. In the event of a dosing error, the sponsor should be notified immediately. Whether or not the medication error is accompanied by an AE, as determined by the investigator, it is captured on an adverse event (AE) CRF

page as well as any AEs associated with the medication error (refer to [Section 8](#) of main LTE protocol).

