5.9.1. Dosage Reduction and Withholding

All subjects will receive open-label tofacitinib 5 mg BID and MTX or matching placebo upon entry into the sub-study. Dosage of both tofacitinib and MTX (predetermined dose as described in Sub-Study [Section 5.1](#)) must remain stable for the duration of the sub-study.

If the investigator deems it necessary to withhold any of the study medications to treat a non-serious infection or other medical condition, temporary withholding is permitted for up to 5 days of tofacitinib and 1 weekly dose of MTX. If the study drug administration is interrupted for more than 5 days or 1 weekly dose of MTX due to a medical reason, the investigator must contact the Pfizer study clinician for approval.

Temporary withholding of study medication, as described above, is permitted once during the study without obtaining prior approval from Pfizer Study clinician. Any additional request(s) for temporary withholding of study drug require(s) documented approval by the Pfizer Study Clinician.

Dosage of tofacitinib and/or MTX may be temporarily discontinued for up to 14 consecutive days or 2 weekly doses, for severe cytopenias, for infections which meet criteria for serious infections (ie, those requiring parenteral antimicrobial therapy or hospitalization), for surgical procedures or other moderately severe AEs.

Treatment with tofacitinib will be discontinued and the subject withdrawn from this study due to safety issues as defined in [Appendix 4.3](#).

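### Minor dosing-safety gap: the observed first methotrexate/placebo dose at sub-study entry is not conditional on the date of the last personal methotrexate dose

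*Protocol*

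**What the plan says.** All references are to Protocol Appendix 10 unless stated.

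- **Visit day.** Section 6 has subjects complete the combined Switch/Baseline visit "on the same day of the scheduled A3921092 study visit at or after Month 24". It is not linked to the day of the week on which the subject takes MTX.
- **End of personal MTX.** Section 5.4 says that at enrolment, which it identifies with this visit, "subjects must discontinue the use of their personal (commercial) supply of MTX".
- **First blinded dose.** Sections 6.1.1, 6.1.2 and 6.1.3 all end with the same instruction: "Observe subject taking the study drugs (tofacitinib and MTX or placebo) and record the dosing in the dosing log CRF". Section 5.9.1 agrees: "All subjects will receive open-label tofacitinib 5 mg BID and MTX or matching placebo upon entry into the sub-study".
- **Weekly schedule.** The sponsor-supplied MTX or placebo "must be administered orally once a week (the same day of the week) in a predetermined dose" (5.4).
- **Dose.** "The dose of MTX must be the same oral dose as taken prior to sub-study entry" (5.1), within 7.5 to 20 mg a week. Criterion 5 in 4.1 requires that dose to have been stable for 4 weeks before entry.
- **Errors.** Section 5.4 treats intake "by the wrong subject, at the wrong time, or at the wrong dose" as a medication error to be reported.

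No section asks for the date of the last personal MTX dose before the observed dose, or sets a minimum interval between the two.

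**The concern.** Subjects arrive on stable weekly oral MTX, so a personal dose within the past week is expected. The handover from personal to blinded supply takes place on a day fixed by the LTE calendar, and the site is told to watch the capsules being swallowed that day. In the placebo arm this does no harm. In the MTX arm it can put a second full weekly dose on top of a recent one, contrary to the once-weekly intent of 5.1 and 5.4.

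At stake is subject safety at a single time point, not an estimate or an error rate. Because the capsules are blinded, the site cannot take the precaution for MTX-arm subjects only. The protocol has to set one rule for everyone.

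The sponsor writes spacing rules elsewhere. Main protocol section 3 puts the first tofacitinib dose at least 1 week after the last injection in A3921091. Section 5.4 of the appendix says when a late tofacitinib dose is to be skipped. The MTX handover has no equivalent.

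**Working it through.** The plan gives no figure on this point, so the check is interval arithmetic.

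**1. Doses.** Sub-Study Table 3 gives 3 to 8 capsules of 2.5 mg: 3 × 2.5 = 7.5 mg, rising to 8 × 2.5 = 20 mg. This reproduces the stated range. Two weekly doses total 2 × (7.5, 10, 12.5, 15, 17.5, 20) = 15, 20, 25, 30, 35 or 40 mg.

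**2. Interval as written.** Let k be the days from the last personal dose to the visit. The observed dose is taken on the visit day, so the interval is k.

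| k (days) | 0 | 1 | 2 | 3 | 4 | 5 | 6 | 7 |
|---|---|---|---|---|---|---|---|---|
| Interval as written | 0 | 1 | 2 | 3 | 4 | 5 | 6 | 7 |
| Under 7 days? | yes | yes | yes | yes | yes | yes | yes | no |
| Deferral d = 7 − k under a 7-day rule | 7 | 6 | 5 | 4 | 3 | 2 | 1 | 0 |

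The k = 0 and k = 7 columns are the same weekday. The visit falls on the usual MTX day, and the personal dose either has or has not already been taken at home. With the rule, the interval is k + (7 − k) = 7 days.

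**3. How often per subject.** Once. Later capsules follow a fixed weekday, and 12 months of 4 weeks give about 48 weekly doses.

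**4. Why to count from the last dose date rather than to the next usual day.** Suppose the usual day is Monday, the last dose was taken late on Wednesday, and the visit is on Friday (k = 2). Waiting for Monday gives a 5-day interval. The 7-day rule gives the following Wednesday, 5 days after the visit.

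**5. Can the visit be booked on the MTX day?** Months 24, 27, 30, 33 and 36 all have a ±10-day window (main protocol 6.2.2 to 6.2.4). That is 10 + 10 + 1 = 21 days, which contains each weekday three times.

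**6. Side effect on capsule compliance.** Month 1 has target day 29 (SAP Appendix 6, 7.4) ± 7 days, so the visit falls on days 22 to 36. Count weekly doses due before visit day V, with the first capsule on day 1 + d:

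- d = 0: 3 doses for V = 22, 4 for V = 23 to 29, 5 for V = 30 to 36.
- d = 6: 3 doses for V = 23 to 28, so 3/4 = 75%. At V = 29 there are 4, so 4/4.
- d = 7: 2 doses at V = 22, so 2/3 = 67%; 3 doses for V = 23 to 29, so 3/4 = 75%; 4 doses for V = 30 to 36, so 4/5 = 80%.

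If compliance were counted from Day 1, a subject who followed the rule exactly could fall below the 80% counselling line in 5.5. Counting from the first capsule day removes this.

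**The case against.** The strongest reply is that the trial may already control this outside the protocol body. Section 5.4 sends subjects to a dosing card, and 5.1 adds training and written instructions. None of these is in the documents. That stands as a limit: the finding covers the protocol text only, and it cannot be said that the trial lacks the control.

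The second reply is that the protocol's general terms already forbid a doubled dose. It points to weekly dosing on a fixed day, an unchanged dose of at most 20 mg a week, local standard of care (4.1, criterion 5) and the local label (main protocol 4.1.1, criterion 5). Concomitant treatments are also reviewed at the entry visit. These provisions show the intent and a careful site would act on them. But the weekly rule in 5.4 is written for the sponsor-supplied capsules. If it is read as keeping the subject's existing day, it conflicts with an observed dose on any other day. Recording treatments triggers no dosing rule, and the medication-error clause acts only after the capsules are swallowed. None of this overrides a specific visit instruction.

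A reader might also infer that 5.1 stands in the way of deferring the capsule, since "Temporary withdrawals of any of the sub-study drugs (tofacitinib and methotrexate/placebo) are only permitted if required" by safety concerns. The documents do not support that. Avoiding a doubled weekly MTX dose is itself a safety concern, so an investigator could defer under 5.1. The gap is that nothing prompts the investigator to ask.

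**Conclusion.** The point stands as minor. Followed as written, the visit lists can give an MTX-arm subject whose last personal dose was 0 to 6 days earlier two weekly doses less than 7 days apart. The total is 15 to 40 mg, once, at entry. Folate is required throughout, and each dose is one the subject already takes.

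Three stronger readings should be resisted.

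- **A frequency.** Six of the seven weekdays other than the MTX day give k = 1 to 6 is not what the calendar yields as a rate: there are seven possible weekdays, six of which are not the MTX day. With even spacing of visits and no same-day home dose, one could compute 90 × 6/7 ≈ 77 of the 90 planned MTX-arm subjects. The documents give no distribution of visit days against MTX days, and sites may already book around it. The supportable range is 0 to 90.
- **Harm to the results.** Nothing in the documents supports an effect on the Month 6 comparison, the sample size, laboratory values or blinding, and none is claimed.
- **A SAP defect.** The observed tofacitinib dose alone still fixes Day 1 and entry to the full analysis set (SAP Appendix 6, 4.1 and 7.4). No SAP change is needed.

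**What to change.** In Appendix 10, section 5.4 and each of 6.1.1 to 6.1.3, add:

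> Schedule the Switch/Baseline visit, within its ±10-day window, on the subject's usual MTX day, with no personal MTX taken that day. Confirm and record the date of the last personal MTX dose before dosing. If it is less than 7 days earlier, observe tofacitinib only and have the first blinded MTX/placebo capsules taken 7 days after that dose, in both arms alike.

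In 5.9.1, state that this deferral is not a temporary withholding. No weekly dose is skipped, so it should not use up the single withholding allowed without prior approval. In 5.5, count capsule compliance from the first capsule day.

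The cost is three sentences in 5.4 and the three visit lists, one dosing-log field, and one line each in 5.9.1 and 5.5. The downside is some constraint on scheduling. In the fallback case the first capsule dose is also unobserved and falls 1 to 7 days after Day 1. Booking on the MTX day keeps the observed dose and should make the fallback uncommon.
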